2.1. Analysis Phases and Visit Windows

2.1.1. Analysis Phase

The analysis phases are defined in [Table 1](#) below.

Table 1: Analysis Phases Start and End Dates

Analysis phase	Start date	End date
Screening	The date of signing the informed consent	1 day before the first study agent intake
Double-Blind (DB) Study Intervention	Date of first study agent intake	
If participant did not withdraw from the study and did not discontinue treatment early prior to the projected/actual Week 52 Visit date:
 
Min(Date of Week 52 study agent intake – 1 day, cut-off date*)
 
Otherwise:
 
[Min (Early study withdrawal visit date, study agent discontinuation date) + 5 days^a] or cut-off date*, whichever occurs first

Open-Label (OL) Study Intervention	
If participant has a projected/actual Week 52 Visit date:
 
 – End date of DB study intervention phase + 1 day 
Otherwise:
 
 – Missing 	
If participant did not withdraw from the study prior to the projected/actual Week 144 (Arm 1)/Week 148 (Arm 2) Visit date and did not discontinue treatment early prior to the projected/actual Week 140 (Arm 1)/Week 144 (Arm 2) Visit date:
 
[Min (Date of Week 144 Visit (for Arm 1) or / Date of Week 148 Visit (for Arm 2))+ 5 days^a] or cut-off date*, whichever occurs first
 
if participant withdrew from the study or discontinued treatment between projected/actual Week 52 Visit date + 1 day and projected/actual Week 144 (Arm 1)/Week 148 (Arm 2) Visit date:
 
[Min (Early study withdrawal visit date, study agent discontinuation date)+ 5 days^a] or cut-off date*, whichever occurs first

Follow-up	
If participant did not withdraw informed consent during DB or OL study intervention phases
 
Max (End date of DB study intervention phase, End date of OL study intervention phase) + 1 day
 
Otherwise:
 
Missing
	
If participant entered the Follow-up phase:
 
Max [early study withdrawal visit date, study completion date] or cut-off date, whichever occurs first.
 
Otherwise:
 
Missing

*Cut-off dates will be defined to match the prespecified timepoints for IDMC safety monitoring, interim analysis, the primary analysis and the final analysis, respectively.

^a: Addition of 5 days is only applicable for Adverse Events and Concomitant Medications

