4.6. Extent of Exposure

Extent of exposure to study treatments will be summarized and presented based on the safety analysis set. The total duration of exposure during the DB and OL study intervention phases will

be calculated by each study treatment (JNJ-3989/placebo and NA) separately and summarized descriptively by intervention arm. The duration of treatment with NA will be summarized also for the follow up phase for participants with presence of compensated cirrhosis at screening by intervention arm.

Because of the different route and frequency of treatment administration across the 2 study treatments (for JNJ-3989/placebo one subcutaneous injection once every 4 weeks, and for NA once daily tablet), the total duration of exposure (weeks) will be calculated by analysis phase for each agent as follows:

- For the DB study intervention phase:
 - JNJ-3989/placebo: $[\text{Min} ((\text{Date of last injection in the DB intervention phase} + 27 \text{ days}), \text{Early study withdrawal visit date, cut-off date}) - \text{date of first injection in the DB phase} + 1] / 7$
 - NA: $[\text{Min} (\text{Date of the last NA administration in the DB phase, Date of discontinuation from NA, Early study withdrawal visit date, cut-off date}) - \text{first drug administration date in the DB phase} + 1] / 7$
- For the OL study intervention phase (only for participants with non-missing OL phase start date, as defined in Section 2.1.1):
 - JNJ-3989: $[\text{Min} ((\text{Date of last injection in the OL phase} + 27 \text{ days}), \text{Early study withdrawal visit date, cut-off date}) - \text{Week 52 study agent intake date} + 1] / 7$
 - NA: $[\text{Min} (\text{Date of the last NA administration in the OL phase, Date of discontinuation from NA, Early study withdrawal visit date, cut-off date}) - \text{Week 52 NA intake date} + 1] / 7$

Cutoff dates will be defined to match the prespecified timepoints for IDMC periodical data reviews, interim analyses and the primary and final analyses, respectively (see Section 3.3).

The number and percentage of participants who skipped any dose of JNJ-3989/placebo or NA will be summarized separately for each study treatment by intervention arm during the DB and OL study intervention phases, separately. Additionally, the number and percentage of participants who missed 2 or more consecutive JNJ-3989/placebo injections, or who missed more than 5 doses of NA within a four-week period will be presented.

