For each lab parameter, a worst-case analysis will be performed by using the worst abnormality and/or worst toxicity grade lab value and time point per participant. The worst toxicity case is the value associated to the highest toxicity grade and is derived per parameter and toxicity direction (low / high). Worst-case will be derived within each phase, including unscheduled assessments. For abnormalities, in case the same subject has both abnormalities (low and high) for the same lab test within the same phase, the participant will be counted in the analysis for both toxicity directions (abnormally high and low).

Imputation rules:

In case continuous laboratory results are not numerically expressed, but as a character (e.g. ‘less than 2’, ‘>25’), these results will be numerically imputed as follows:

- If the analysis result contains '<' then the result will be multiplied by 0.999 (e.g. <6.1 becomes 6.0939).
- If analysis result contains '>' then the result will be multiplied by 1.001 (e.g. >6.1 becomes 6.1061).
- If analysis result contains '≤' or '≥' then only the numeric portion of the result will be used.

This also applies to normal limits expressed as such.

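### For participants who stop JNJ-3989/placebo early but stay in the study, Table 1 can close the treatment phase before the exposure window of SAP 4.6 ends, so by-phase safety tables may report exposed-time events under follow-up.

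*SAP*

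**What the plan says.** SAP 2.1.1, Table 1, gives one rule to participants who discontinue early in either treatment phase. The phase ends at "Min (Early study withdrawal visit date, study agent discontinuation date"), with 5 days added and the data cut-off as a cap. The footnote restricts the extension: "Addition of 5 days is only applicable for Adverse Events and Concomitant Medications". Laboratory, ECG and vital-sign data therefore get no extension. Follow-up starts the next day.

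Completers are treated differently. The double-blind phase runs to the day before the Week 52 injection. The open-label phase ends at "Min (Date of Week 144 Visit (for Arm 1) or / Date of Week 148 Visit (for Arm 2))+ 5 days", with the same restriction on the 5 days.

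Section 4.6 describes the regimen as "for JNJ-3989/placebo one subcutaneous injection once every 4 weeks". It counts double-blind exposure from the first injection to 27 days after the "Date of last injection in the DB intervention phase", and open-label exposure in the same way. That end date is capped by the study withdrawal visit and the cut-off, but not by discontinuation of the agent.

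The phase dates drive the safety output. Section 6 presents safety by phase and arm, 6.1.2 assigns adverse events to a phase by start date, and 6.1.3 summarises events of special interest, including ALT/AST elevations, by phase. For laboratory data 6.2.1 states: "Worst-case will be derived within each phase, including unscheduled assessments".

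**The concern.** The SAP applies two on-treatment windows to the same injection. Section 4.6 treats a full 4-week interval as exposed. Table 1 can close the phase well inside that interval, but only for people who stop early. They are also the people most likely to have stopped for toxicity, and ALT elevation is the risk that led to the Part 1 interim analyses and to added discontinuation criteria. Under 3.3.1, selected team members could have sites apply those criteria to Part 1 patients receiving active treatment, so the shorter window may fall more heavily on Arm 1.

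At stake is the double-blind phase, the only one with a concurrent placebo arm. A further ALT rise, a bilirubin rise or a serious event later in the dosing interval would leave that comparison and appear under follow-up.

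**Working it through.** **Inputs.** Injections every 4 weeks (4.6). Scheduled injection counts of 13 double-blind, 23 open-label in Arm 1 and 24 open-label in Arm 2 (4.7). Target day = 7 × week + 1 (Table 2): Week 48 = 337, Week 52 = 365, Week 140 = 981, Week 144 = 1009. By the same formula Week 148 = 1037.

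**The plan's own figures.** Injections at Weeks 0–48 number 13, at Weeks 52–140 number 23, and at Weeks 52–144 number 24, so all three counts reproduce. The last open-label injection is at Week 140 (Arm 1) or Week 144 (Arm 2). The 4.6 formula on the nominal schedule gives:
- double-blind: (337 + 27 − 1 + 1)/7 = 52.0 weeks
- open-label Arm 1: (981 + 27 − 365 + 1)/7 = 92.0 weeks
- open-label Arm 2: (1009 + 27 − 365 + 1)/7 = 96.0 weeks

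**Completers, in days after the last injection.**
- Double-blind: the phase ends on day 365 − 1 = 364, and 364 − 337 = 27. This agrees exactly with 4.6.
- Open-label: 1009 − 981 = 28 (Arm 1) and 1037 − 1009 = 28 (Arm 2) for laboratory data; 28 + 5 = 33 for adverse events.

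**Early stoppers who stay in the study.** Let d = discontinuation date minus last injection date. The phase ends at day d + 5 for adverse events and day d for laboratory data. Exposure runs to day 27. Days that are exposed but labelled follow-up are therefore max(0, 27 − (d + 5)) for adverse events and max(0, 27 − d) for laboratory data.

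| d | AE phase ends (day) | Lab phase ends (day) | AE days moved | Lab days moved |
|---|---|---|---|---|
| 0 | 5 | 0 | 22 | 27 |
| 7 | 12 | 7 | 15 | 20 |
| 14 | 19 | 14 | 8 | 13 |
| 21 | 26 | 21 | 1 | 6 |
| 22 | 27 | 22 | 0 | 5 |
| 27 | 32 | 27 | 0 | 0 |
| 28 | 33 | 28 | 0 | 0 |

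Adverse events starting on days d + 6 to 27, and laboratory values on days d + 1 to 27, are the ones relabelled.

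**Effect on an incidence.** Safety is pooled over both parts (Section 6), and the total is 52 (1.2). At 4:1, Arm 1 has about 52 × 4/5 = 41.6 participants. One participant whose only qualifying double-blind event is moved lowers the Arm 1 percentage by 1/41.6 = 2.4 points.

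**The case against.** The strongest objection is that the size rests on a date the SAP never defines. Section 4.6 lists the last NA administration and the discontinuation of NA as separate items, which suggests, without proving, that discontinuation is recorded separately from the last dose. If it is recorded when the next injection was due, nothing moves. This stands, and it is why the size is given as a range.

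A reader might infer that the double-blind phase loses the worst values of those who stopped for toxicity. The documents do not support that:
- If the date is that of a decision to stop, the value that prompted it falls on or before that date and stays in phase. Only later values can move.
- Moved adverse events remain treatment-emergent, because the definition in 6.1.1 has no end date, and they still appear by arm under follow-up.
- The flare and ALT-elevation endpoints are not cut at the phase end. For HBV endpoints, 5.5 counts a participant still taking NA as on-treatment, 5.5.1.1.11 follows an on-treatment biochemical flare until ALT/AST has halved from its peak even if treatment stops, and 5.5.1.1.12 ends an elevation on ALT/AST criteria.
- The safety summaries are descriptive percentages of participants, with no exposure-adjusted rates, so no denominator is distorted.

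Participants who leave the study altogether are largely unaffected, since 4.6 also caps exposure at the withdrawal visit.

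A reader might also infer that follow-up Day 1 should be moved for all data. Table 2 takes end of treatment as the last post-baseline visit in a treatment phase, and HDV relapse and time to relapse (5.5.1.1.4, 5.5.1.3.2.1) are measured from it. Moving the phase end for all data would change those efficacy derivations.

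What survives is that Table 1 and 4.6 disagree for early stoppers, and that the by-phase adverse-event, special-interest and worst-grade laboratory tables follow Table 1.

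**Conclusion.** The inconsistency is real and affects by-phase safety tables for participants who stop the agent and remain in the study. Its size runs from 22 adverse-event days and 27 laboratory days per such participant (d = 0) to none (d of at least 22 and 27 respectively). Each Arm 1 participant whose only qualifying double-blind event falls in the gap lowers that incidence by about 2.4 points, assuming about 42 in Arm 1; the SAP does not give the actual arm sizes. The number of participants affected cannot be obtained from the SAP.

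Where events move, the double-blind tables can understate toxicity in those who stopped because of it. The SAP does not show that this will happen, or that any event disappears from the report. The primary endpoint is not touched by this point, because stopping treatment before Week 48 already counts as non-response (5.3.2). The point deserves correction because an undefined date leaves the programmer to choose the window on the trial's main safety question.

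**What to change.** 1. Define the study agent discontinuation date in 2.1.1: the last injection, the decision to stop, or the first injection not given.
2. For safety tables only (adverse events, laboratory data, ECG, vital signs), end the treatment phase of early stoppers at min(max(study agent discontinuation date, last injection + 27 days), withdrawal visit, cut-off). Apply the 5-day extension for adverse events as for open-label completers, still capped at the cut-off. The inner maximum prevents the rule from shortening the window when discontinuation is recorded late. At d = 0 the phase then ends on day 27 for laboratory data and day 32 for adverse events, within one day of open-label completers (28 and 33).
3. Leave efficacy end of treatment and the follow-up windows unchanged, and state that the safety phase flag is separate.

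The cost is a short SAP amendment and one added date derivation from dates that Table 1 and 4.6 already use; no new data are needed. The downsides are that treatment-phase incidences may look slightly less favourable, and that safety and efficacy phase flags will differ for a few participants, which a table footnote should explain.

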2.1.2. Relative Day by Study Phase

An analysis relative day (ADY) will be calculated for all assessments at all visits for each participant.

2.1.2.1. Double-Blind Study Intervention Relative Day

The Double-Blind (DB) Study intervention start date (DB Day 1) is defined as the date of first study agent intake. All efficacy and safety assessments during the DB study intervention phase will be assigned a day relative to this date.

The study day in the Double-Blind intervention phase (DB ADY) is defined as:

$$DB\ ADY = \text{visit date} - DB\ \text{start date} + 1$$

for visits on or after Day 1, and

$$DB\ ADY = \text{visit date} - DB\ \text{start date}$$

for visits before DB Day 1 (Screening phase).

There is no 'Day 0'.

2.1.2.2. Follow Up Relative Day

Follow Up (FU) start date (FU Day 1) is defined in [Table 1](#). All efficacy and safety assessments during the FU phase will be assigned a day relative to this date.

The FU study day in the FU treatment phase (ADY) is defined as:

$$FU\ ADY = \text{visit date} - FU\ \text{start date} + 1$$

2.1.3. Analysis Visits and Time Points

All visits for all assessments (safety, efficacy or PK) will be uniquely allocated within each phase to an analysis time point based on the analysis relative day (ADY) compared with the target days based on [Table 2](#). All assignments will be made in chronological order. Once a visit is assigned to a visit window (time interval in [Table 2](#)), it will no longer be used for a later time point except for the end of treatment (EOT) and the end of study (EOS) visits. If two or more visits fall within the same interval in the same phase, only one measurement will be selected for the analysis time point per phase in order to have only one evaluation per participant. The following rules will be applied:

1. The measurement closest to the target day in that phase will be used.
2. If the measurements fall equidistant from the target day, the last measurement in chronological order within the interval will be used per phase.
3. If there are two or more measurements on the same day, then the last measurement in chronological order will be used. If the time of the assessment is not available the highest record/sequence number will be selected.

The listings will include all measurements, also those multiple assessments within the same visit window/phase.

End of treatment (i.e. EOT) and end of study (i.e. EOS) time points will be included in all analysis over time unless stated otherwise.

Note: For the selection of the patient-reported outcome (PRO) measurements the above algorithm needs to be performed on the entire questionnaire (filled in at a specific date and time) and not on the individual questions /items (i.e., not mixing answers from different questionnaires)

Table 2 provides the analysis time points, time intervals for each visit per analysis phase.

Table 2: Analysis Time Point and Time Intervals by Analysis Phase

Phase	Target day	Analysis time point (Week)	Analysis time point (label)	Time interval (days) for Arm 1	Time interval (days) for Arm 2 ^(a)
Screening	-28 to -1	-1	Screening	<0	
Double-Blind (DB) Study Intervention	1	0	Baseline	Pre-dose ; 1	
	15	2	Week 2	[2,22]	
	29	4	Week 4	[23, 43]	
	57	8	Week 8	[44, 71]	
	85	12	Week 12	[72, 99]	
	113	16	Week 16	[100, 127]	
	141	20	Week 20	[128, 155]	
	169	24	Week 24	[156, 183]	
	197	28	Week 28	[184, 211]	
	225	32	Week 32	[212, 239]	
	253	36	Week 36	[240, 267]	
	281	40	Week 40	[268, 295]	
	309	44	Week 44	[296, 323]	
	337	48	Week 48	[324,351]	
Open-Label (OL) Study Intervention	365	52	Week 52	[352, 372]	
	379	54	Week 54	[373, 386]	
	393	56	Week 56	[386, 407]	
	421	60	Week 60	[408, 435]	
	449	64	Week 64	[436, 463]	
	477	68	Week 68	[464, 491]	
	505	72	Week 72	[492, 519]	
	533	76	Week 76	[520, 547]	
	561	80	Week 80	[548, 575]	
	589	84	Week 84	[576, 603]	
	617	88	Week 88	[604, 631]	
	645	92	Week 92	[632, 659]	
	673	96	Week 96	[660, 687]	
	701	100	Week 100	[688, 715]	
	729	104	Week 104	[716, 743]	
	757	108	Week 108	[744, 771]	
	785	112	Week 112	[772, 799]	
	813	116	Week 116	[800, 827]	
	841	120	Week 120	[828, 855]	
	869	124	Week 124	[856, 883]	
	897	128	Week 128	[884, 911]	
	925	132	Week 132	[912, 939]	
953	136	Week 136	[940, 967]		
981	140	Week 140	[968, 995]		
1009	144	Week 144 ^(b)	Not Applicable	[996, 1023]	

Phase	Target day	Analysis time point (Week)	Analysis time point (label)	Time interval (days) for Arm 1	Time interval (days) for Arm 2 ^(a)
	last visit during the intervention phase	149*	EOT ^(b)		
Follow-Up (FU)	15	150	Follow-up Week 2	[1, 22]	
	29	152	Follow-up Week 4	[23,36]	
	43	154	Follow-up Week 6	[37, 50]	
	57	156	Follow-up Week 8	[51, 71]	
	85	160	Follow-up Week 12	[72, 99]	
	113	164	Follow-up Week 16	[100, 127]	
	141	168	Follow-up Week 20	[128, 155]	
	169	172	Follow-up Week 24	[156, 190]	
	211	178	Follow-up Week 30	[191, 232]	
	253	184	Follow-up Week 36	[233, 274]	
	295	190	Follow-up Week 42	[275, 316]	
	337	196	Follow-up Week 48	[317, +∞]	
		last visit in the study	999*	EOS	

(a) Participants randomized to Arm 2 (placebo + NA) will have additional assessments during the OL phase at Week 54 and Week 144. See Protocol Section 1.3.2 for more details

(b) For participants who completed the OL phase (see Table 1), EOT corresponds to Week 144 Visit Date for Arm 1 and Week 148 for Arm 2

*End of treatment (EOT) visit will be the last post-baseline visit in double-blind or open-label phase, and End of study (EOS) visit (last available data during the follow-up) will be the last visit in the study.

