5. EFFICACY

The primary analysis set will be the ITT analysis set (see definition in Section 2.3), unless specified otherwise. Efficacy assessments over time will be performed at the analysis time points defined in Section 2.1.3. However, the use of the mITT analysis set (instead of ITT) in the efficacy analyses will be determined based on the impact of the COVID-19 or similar pandemics and assessed prior to the database lock for the first IA during DB study intervention phase.

All efficacy data will be summarized by study Parts 1 and 2, as well as for the whole study data overall:

- For DB study intervention phase: by study intervention arm over time (when applicable), as well as by study part (1 and 2).
- For OL study intervention and Follow-up phases: by study intervention arm over time and by study part 1 and 2. Additional selected efficacy analyses will be conducted to compare the OL study intervention data from Week 52 to Week 148 in Arm 2 with data from the first 96 weeks of DB study intervention in Arm 1 (i.e same duration of exposure to JNJ-3989+NA in both arms). See Section 5.5.1.4 for more details.

Subgroup analyses will be conducted on Part 2 data alone as well as combined data (Part 1 and Part 2) to leverage the total sample size of the entire study. Subgroup analyses will be performed if their size is at least 10% of the total sample size. All analyses will be presented only in a descriptive fashion.

For OL intervention and FU study phases, all efficacy data will be presented only descriptively, and no formal testing will be performed.

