5.5. Other Secondary Endpoints

Other secondary endpoints will be summarized descriptively by intervention arm, by study phase (unless specified otherwise), timepoint and study part. No imputation rule will be used in case of missing data and the analysis will be based on observed cases. Statistical analyses of selected other secondary endpoints will be done with no adjustment for multiplicity.

The following on and off-treatment periods will be used for all secondary efficacy endpoints:

- For all HBV endpoints:
 - **On-treatment** will be defined as the time periods in which the participant receives any of the study interventions (JNJ-3989/placebo and/or NA).
 - **Off-treatment** will be defined as the periods when the participants do not receive any of the study interventions (JNJ-3989/placebo and NA).
- For all HDV endpoints:
 - **JNJ-3989 on-treatment** will be defined as the time period in which the participant receives JNJ-3989/placebo (regardless of continuing NA treatment).
 - **JNJ-3989 off-treatment** will be defined as the time period in which the participant is not receiving JNJ-3989 (regardless of continuing NA treatment).

The following on and off-treatment nadirs will be used for all secondary efficacy endpoints:

- **On-treatment nadir** will be defined as the lowest value during the on-treatment period up to the time of assessment.
- **JNJ-3989 on-treatment nadir** will be defined as the lowest value during the JNJ-3989 on-treatment period up to the time of assessment.
- **Off-treatment nadir** will be defined as the lowest value during the off-treatment period up to the time of assessment.
- **JNJ-3989 off-treatment nadir** will be defined as the lowest value during the JNJ-3989 off-treatment period up to the time of assessment.
- **Overall nadir** will be defined as the lowest value collected during the study up to the time of assessment.

A confirmed criteria means that the criteria should be fulfilled at 2 or more consecutive time points or at the last observed time point.

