The start date of a confirmed off-treatment biochemical flare is defined as the first date of two consecutive visits with ALT and/or AST \geq 3x ULN and \geq 3x nadir (ie, lowest value observed up to the start of the flare). The end date of the same off-treatment biochemical flare is defined as the first date when there is a 50% reduction from the peak ALT and/or AST level or the date of treatment restart (ie JNJ-3989 and/or NA), whichever comes first.

- 1 (Yes) = confirmed ALT and/or AST \geq 3x ULN and \geq 3x nadir (ie, lowest value observed up to the start of the flare)
- 0 (No) = otherwise

c) On-treatment HBV biochemical flare is defined as follows:

The start date of a confirmed on-treatment biochemical flare is defined as the first date of two consecutive visits with ALT and/or AST \geq 3x ULN and \geq 3x nadir (ie, lowest value observed up to the start of the flare). The end date of the same on-treatment biochemical flare is defined as the first date when there is a 50% reduction from the peak ALT and/or AST level, regardless of stopping JNJ-3989 and/or NA.

- 1 (Yes) = confirmed ALT and/or AST \geq 3x ULN and \geq 3x nadir (ie, lowest value observed up to the start of the flare)
- 0 (No) = otherwise

d) HBV Clinical flare is defined as follows:

A HBV clinical flare occurs either when a HBV virologic flare and off-treatment HBV biochemical flare overlap in time or when a HBV biochemical flare starts within 4 weeks following the end of a HBV virologic flare.

The start date of a HBV clinical flare is defined as the minimum start date of the HBV virologic flare and HBV biochemical flare. The end date of a HBV clinical flare is defined as the maximum end date of the HBV virologic flare and HBV biochemical flare, ie, the later date between HBV DNA returns to ≤ 200 IU/mL (or $\leq 1 \log_{10}$) and 50% reduction from the peak ALT and/or AST level reached during the HBV biochemical flare.

- 1 (Yes) = confirmed HBV DNA $>$ peak threshold (for derivation 1 of virologic flare) or HBV DNA increase from end of treatment $>$ peak threshold (for derivation 2 of virologic flare) and confirmed ALT and/or AST $\geq 3x$ ULN and $\geq 3x$ nadir (ie, lowest value observed up to the start of the flare)
- 0 (No) = otherwise

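### A same-window re-test cannot confirm HDV or HBV breakthrough or HDV relapse, and the SAP leaves open whether it can confirm ALT/AST flares and elevations

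*SAP*

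**What the plan says.** **Window rule (Section 2.1.3).** The scope is general: "All visits for all assessments (safety, efficacy or PK) will be uniquely allocated within each phase to an analysis time point". Several visits may fall in one interval, in which case "only one measurement will be selected for the analysis time point per phase in order to have only one evaluation per participant". The first selection rule is "The measurement closest to the target day in that phase will be used". Values not selected survive in listings: "The listings will include all measurements, also those multiple assessments within the same visit window/phase".

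**Link to efficacy (Section 5).** "Efficacy assessments over time will be performed at the analysis time points defined in Section 2.1.3".

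**General meaning of confirmed (Section 5.5).** It means that "the criteria should be fulfilled at 2 or more consecutive time points or at the last observed time point". HDV RNA breakthrough (5.5.1.1.3), off-treatment HDV RNA relapse (5.5.1.1.4) and HBV breakthrough (5.5.1.1.9) use the word confirmed and add no rule of their own. The same holds for the HDV RNA component of the off-treatment HDV clinical flare (5.5.1.1.5).

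**Flares and elevations (5.5.1.1.11 and 5.5.1.1.12).** These carry a separate rule, for example "the first date of two consecutive visits with ALT and/or AST" above the stated multiples of ULN and nadir.

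**Unscheduled values.** For laboratory data they are brought in expressly only for the safety worst-case analysis in Section 6.2.1: "Worst-case will be derived within each phase, including unscheduled assessments".

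**The concern.** A re-test shortly after an abnormal value is the natural way to confirm an event. Under a one-value-per-window rule the two results share a window, and one of them disappears before confirmation is judged. A short episode that was in fact measured twice is then recorded as unconfirmed.

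At stake are event counts among the other secondary endpoints, and the classification of participants by ALT elevation. The SAP's Amendment 5 rationale links the temporary enrolment halt to ALT elevations. Section 5.6.1.8 tabulates efficacy, safety and baseline characteristics by ALT elevation status, so a change in that status carries through those tables. With 22 participants in Part 1 and 30 in Part 2, a few reclassified participants would be visible.

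**Working it through.** The SAP gives no figure to reproduce here. The check applies Table 2 and the selection rule to hypothetical series.

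**1. How far the window reaches past an on-target visit.** Reach = upper limit of the window − target day.

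| Window | Target day | Interval | Reach (days) |
|---|---|---|---|
| Week 2 | 15 | 2–22 | 22 − 15 = 7 |
| Week 8 | 57 | 44–71 | 71 − 57 = 14 |
| Week 48 | 337 | 324–351 | 351 − 337 = 14 |
| Week 52 | 365 | 352–372 | 372 − 365 = 7 |
| FU Week 4 | 29 | 23–36 | 36 − 29 = 7 |
| FU Week 12 | 85 | 72–99 | 99 − 85 = 14 |
| FU Week 24 | 169 | 156–190 | 190 − 169 = 21 |
| FU Week 30 | 211 | 191–232 | 232 − 211 = 21 |

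Target days are 14 days apart at Weeks 2–4, Weeks 52–54–56 (Week 54 in Arm 2 only) and FU Weeks 2–8. They are 42 days apart from FU Week 24 and otherwise mostly 28.

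**2. Breakthrough, double-blind phase.** Suppose the criterion is met on day 57, met again at a re-test on day 64, and not met on day 85.

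- Days 57 and 64 both lie in 44–71. Their distances from target 57 are 0 and 7, so day 57 is kept and day 64 dropped.
- Day 85 is on target for Week 12 and is kept.
- The selected series is met, not met. The event is not confirmed. With all values in date order it is met, met, not met, and is confirmed.
- If day 85 also meets the criterion, both routes confirm it.
- If day 57 is the last observed time point, that single value counts as confirmed.
- A re-test on day 72 falls in the Week 12 window, 85 − 72 = 13 days from target, and loses to the day-85 visit. Crossing into the next window does not rescue it.

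**3. Flares and elevations.** Take ALT of 1.0, 5.0, 5.0 and 2.5 × ULN on days 29, 57, 64 and 85, with nadir 1.0. If *visits* means actual visits, days 57 and 64 are consecutive and the flare is confirmed. If it means windowed visits, the series is 1.0, 5.0, 2.5 and the flare is not confirmed. The text supports either:

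- For actual visits: Section 2.1.3 itself says that two or more visits can fall in one interval, so a visit is not the same thing as an analysis time point.
- For windowed visits: the section is headed Analysis Visits and Time Points, and Table 2 is introduced as giving intervals for each visit.

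The unit of confirmation also varies across the SAP: time points (5.5), visits (5.5.1.1.11, 5.5.1.1.12), values (HBV DNA peak in 5.5.1.1.11) and measurements (renal markers in 6.3.2). The nadir definitions are not tied to windows.

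**4. Illustration, not a forecast.** Assume on-target visits *g* days apart, an episode of *D* days starting uniformly between visits, and one re-test *r* days after the first qualifying visit, inside its window. Then P(confirmed, windowed) = (*D* − *g*)/*g* and P(confirmed, all data) = (*D* − *r*)/*g*, each limited to 0–1.

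- *g* = 28, *r* = 7, *D* = 28: 0% against (28 − 7)/28 = 75%. With *r* = 14: 0% against 50%.
- *g* = 28, *r* = 7, *D* = 42: (42 − 28)/28 = 50% against 100%.
- *g* = 42, *r* = 7, *D* = 42: 0% against (42 − 7)/42 = 83%.
- *D* = 2*g* (56 or 84 days): 100% either way.

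The re-test lags and episode lengths are assumptions, not SAP figures. The model leaves out the two-week segments and the last-time-point clause. For flares and elevations it applies only under the windowed reading.

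**The case against.** The strongest reply is that window selection serves by-visit summaries only. Section 2.1.3 picks a value for an analysis time point, and Section 5 speaks of assessments over time. Flares and elevations are dated events with their own rule based on visits. That answer stands for flares and elevations to this extent: a reader might infer that same-window ALT re-tests are discarded, but the SAP does not say so, and its literal wording admits them. It does not rescue breakthrough and relapse, because their only confirmation rule is in time points and the window rule covers all assessments.

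A reader might also infer that the ALT safety signal is hidden. The document does not support that. Worst-case laboratory tables include unscheduled values, ALT/AST elevations are adverse events of special interest identified by preferred term, the independent flare panel adjudicates each ALT flare, and listings show every measurement. None of these yields the confirmed elevation status used in 5.6.1.8, so the cover is partial. Nor can one conclude that SAP counts would differ from the events on which participants were managed: that depends on protocol rules not shown here.

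Finally, these are other secondary endpoints in a study that is now descriptive. The primary and key secondary endpoints are judged at Week 48 without confirmation. This limits the severity of the point.

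**Conclusion.** The point holds in two parts.

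- **Breakthrough and relapse.** Followed as written, the SAP cannot use a same-window re-test to confirm HDV RNA breakthrough, HBV breakthrough, off-treatment HDV RNA relapse or the HDV RNA component of the off-treatment HDV clinical flare when the next selected value no longer qualifies. It does accept one value at the last observed time point. Two measured values can therefore count for less than one.
- **Biochemical flares and ALT/AST elevations.** This is an ambiguity, not an established loss. Two programmers could follow the text and report different counts.

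The size is unknown. It depends on how often re-tests were taken and how long episodes lasted, and the SAP gives neither. Only episodes short enough to have ended by the next selected value are affected. This is a clarification to make before the event data are derived, and does not threaten the main results.

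**What to change.** Add to Sections 2.1.3 and 5.5: *Confirmed events (breakthrough, relapse, flares and ALT/AST elevations), nadirs, peaks and event dates are derived from all available measurements, including unscheduled ones, in date order and before window selection. Window selection applies only to by-visit summaries.* Use one unit of confirmation throughout, such as consecutive available measurements, in 5.5, 5.5.1.1.11 and 5.5.1.1.12. Section 6.2.1 already includes unscheduled values for worst-case laboratory results, so the principle is not new to this SAP.

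The cost is SAP wording and minor programming on data already collected. Event counts may rise slightly.
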